12.7 SUSAR Reporting

All SUSARs must be reported to the responsible Regulatory Authorities and Institutional Review Boards/ Ethics Committees (IRBs/ECs) within the required timelines:

- Fatal or life threatening SUSARs will be reported within 7 days of receipt. Any additional information will be reported within 8 days of sending the first report.
- All other SUSARs will be reported within 15 days of receipt.

In addition, other safety issues qualify for expedited reporting where they might materially alter the current risk assessment of NUC-1031 or be sufficient to change NUC-1031 administration or the overall conduct of the study.

NuCana, or Chiltern PV, will notify appropriate regulatory authorities by telephone or fax transmission of any fatal, or life-threatening experience that is determined to be related to the use of the study drug (expedited report) as soon as possible but no later than 7 calendar days after the initial receipt of the information. Initial notification will be followed by a written report within 15 calendar days.

For unexpected events associated with the use of the study drug which are not fatal or life threatening, NuCana or Chiltern PV will notify the regulatory authorities as soon as possible, but no later than 15 days of the initial receipt of information.

The Investigator or Sub-Investigator is responsible for informing the IRB/EC. Copies of SAE correspondence with all Investigators or Sub-Investigators, regulatory authorities, IRBs/ECs and NuCana must be submitted to Chiltern PV for filing.

12.8 Terms and Grading of Events

All AEs and toxicities must be graded according to NCI CTCAE v4.03.

12.9 Pregnancy

Patients who become pregnant should be withdrawn from study treatment immediately. Pregnancies (in a patient or partner) occurring during the study require expedited reporting. A Pregnancy Notification Report should be completed and submitted to Chiltern PV within the same timelines and using the same contact details as an SAE. All reported pregnancies should be followed up and the outcome reported using the Pregnancy Follow-up Report. If the outcome of the pregnancy meets any of the criteria for seriousness, it must also be reported as an SAE.

Examples of pregnancy outcomes that are SAEs include reports of:

- Congenital anomalies or developmental delay, in the fetus or the child.

- Fetal death and spontaneous abortion.
- Suspected adverse reactions in the neonate that are classified as serious.

12.10 Events Exempt from Being Reported as AE/SAEs

12.10.1 Progression of Underlying Disease

Disease progression and resultant death will be captured on the CRF. AEs including hospitalization that are clearly consistent with disease progression will not be reported as individual AE/SAEs. Clinical symptoms of disease progression will only be reported as AEs if the symptom cannot be determined as exclusively due to the progression of the underlying malignancy, or does not fit the expected pattern of progression for the disease under study.

Every effort should be made to document the objective progression of underlying malignancy. In some cases, the determination of clinical progression may be based on symptomatic deterioration. For example, progression may be evident from clinical symptoms, but is not supported by tumor measurements. Or, the disease progression is so evident that the Investigator may elect not to perform further disease assessments.

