6 PATIENT WITHDRAWAL

6.1 End of Treatment

Treatment with NUC-1031 is to be continued until one of the following occurs:

- Progressive Disease (PD) as defined by RECIST criteria. Patients should not discontinue NUC-1031 because of raised CA125 or other clinical signs of PD until PD has been confirmed by RECIST.
- Unmanageable toxicity defined as an AE that is considered by the Investigator to warrant permanent discontinuation of NUC-1031 including the following:
 - AE resulting in a dosing delay of more than 14 days in starting the next cycle, unless the patient is receiving clinical benefit.
 - Clinically significant drug-related AE that recurs despite dose reduction in two consecutive cycles. Patients may continue to receive treatment if the Principal Investigator and Medical Monitor agree that the patient is receiving a clinical benefit and the toxicity is manageable, reversible or transient.
- Lack of further clinical benefit or unfavorable risk/benefit profile as judged by the Investigator.
- Inter-current illness that prevents further administration of NUC-1031.
- Patient withdraws consent from further treatment or for further data collection.
 - If the patient withdraws consent for further treatment, follow-up visits should continue.
 - If the patient withdraws consent for further treatment and data collection, then no additional study visits or data collection should occur.
- Patient requires use of a prohibited concomitant medication or therapy.
- Pregnancy.
- Changes in the patient's condition, which in the opinion of the Investigator, make the patient unsuitable for further treatment with NUC-1031.
- Patient non-compliance.
- Lost to follow-up.
- Patient withdrawal of consent.
- Sponsor request.

All study procedures outlined for the End of Treatment visit are to be completed within 30 days (± 7 days) of the last dose of study drug. The primary reason for study drug discontinuation is to be recorded in the CRF.

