11 TUMOR RESPONSE ASSESSMENTS

11.1 Tumor Measurements and Assessment of Disease Response

Patients must have at least one lesion that can be accurately assessed at baseline by CT, MRI or PET-CT (US only), which is suitable for repeated assessment in order to be eligible for this study. All known or suspected disease sites must be assessed at baseline by either CT, MRI or PET-CT (US only) scan. The same radiological methods at baseline must be used to follow lesions throughout the study. Disease must be measured according to RECIST criteria, with target and non-target lesions identified, measured and followed throughout the study ([Appendix 2](#)). Biopsied lesions should not be designated as target lesions for the purposes of RECIST.

Whenever possible, the same qualified physician will interpret results to reduce variability. Radiographic images will be maintained at the study center, and Investigator's findings will be filed in the patient's source documents.

In addition, digital copies of all radiographic images will be collected and stored in a central radiologic facility in order to allow for independent confirmation of the radiographic imaging results. Instructions for the collection, and submission of images are provided in a separate Imaging Manual.

Tumor measurements and disease response assessments are to be performed every 8 weeks (± 7 days) from C1D1. If the patient stops study treatment for reasons other than radiologically confirmed PD, tumor measurements and disease response assessments should continue every 8 weeks (± 7 days) from C1D1 thereafter until PD is radiologically confirmed.

Tumor measurements and disease response assessments also are to be performed any time disease progression is suspected.

Patients should not discontinue NUC-1031 because of raised CA125 or other clinical signs of PD until PD has been confirmed by RECIST.

CRs and PRs must be confirmed by repeated images at least 4 weeks after initial documentation.

In the case of SD, measurements must have met the SD criteria at least once after study entry at a minimum interval of not less than 6 weeks.

A third-party central imaging vendor will review all study-related imaging. The imaging vendor will not be responsible for assessing images in real-time to inform on patient treatment decisions. This responsibility will remain with the Principal Investigator at the site. Please refer to the Imaging Manual for details on submission and review of images.

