13.5.4 Efficacy Analysis

The primary response evaluation is based upon the determination of response using RECIST ([Appendix 2](#)) by a BICR:

- **ORR** is defined as the number of patients achieving a confirmed response (CR or PR). Number and percentage of patients achieving a response, with confidence intervals, will be provided. In addition, the number and percentage of patients achieving individual best response criteria of CR, PR, SD, PD, or NE will be described.
- **Change from baseline in tumor size** is measured as the percentage change in the total measurements of target lesions from the pre-treatment scan, measured at each scheduled scan.
- **Duration of Overall Response** is measured from the time measurement criteria are first met for CR or PR (whichever is first recorded) until the first date that recurrent or PD is objectively documented (taking as reference for PD the smallest measurements recorded since the treatment started). Only responses that were later confirmed, will be considered when calculating the DoR. For patients who were lost to follow-up without progression or reached the time point of analysis without a known record of death or progression, the duration of response will be censored at the date of last tumor assessment.
- **PFS** is defined as the time from the date of study treatment initiation (start of treatment) to the first date of objectively determined PD or death from any cause. For patients who are still alive at the time of the data cut-off date and without evidence of tumor progression, PFS will be censored at the date of the most recent objective progression-free observation. For patients who receive subsequent anticancer therapy prior to objective disease progression or death, PFS will be censored at the date of the last objective progression-free observation prior to the date of subsequent therapy.

The number of overall censored patients, number of patients with events and Kaplan-Meier estimates median time will be provided. In addition, the results will be presented graphically in Kaplan-Meier plots.

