- **Time to Disease Progression** is measured from the start of the treatment until the criteria for progression are first met, taking as reference the smallest measurements recorded since the treatment started, including the baseline measurements. For patients who were lost to follow-up, or died without progression or reached the time point of analysis without a known record of progression, the time to progression will be censored at the date of last tumor assessment.

The number of overall censored patients, number of patients with events and Kaplan-Meier estimates median time will be provided. The results will also be presented graphically in Kaplan-Meier plots.

- **Disease Control Rate** is defined as the number of patients achieving confirmed response (CR or PR) or SD as best overall response (as defined in RECIST).
- **Best GCIG Overall Response** (CR, PR, SD, PD, NE): number and percentage of patients with responses defined per GCIG criteria will be described.
- **OS** is defined as the time from randomization until death from any cause. All deaths will be included, whether they occur during the study or following treatment discontinuation. For patients who have not died, overall survival will be censored at the date of last contact.

The number of overall censored patients, number of patients with events and Kaplan-Meier estimates median time will be provided. In addition, the results will be presented graphically in Kaplan-Meier plots.

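### Section 12.10.1 lets disease assessments stop when progression is clinically evident, against 6.1, 6.2 and 11.1, so PFS and time to progression may be biased upward

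*Protocol*

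**What the plan says.** **Permission to stop assessing.** Section 12.10.1, within the part on events exempt from AE/SAE reporting, accepts that progression may be judged on symptoms without support from measurements, or that "the disease progression is so evident that the Investigator may elect not to perform further disease assessments". The same paragraph opens with "Every effort should be made to document the objective progression of underlying malignancy".

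**Rules pointing the other way.** Section 11.1: "Tumor measurements and disease response assessments also are to be performed any time disease progression is suspected". It adds that patients who stop treatment without radiologically confirmed progression continue 8-weekly assessments until it is confirmed. Section 6.1: "Patients should not discontinue NUC-1031 because of raised CA125 or other clinical signs of PD until PD has been confirmed by RECIST". Section 6.2 repeats this.

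**Endpoints (13.5.4).** The PFS event is "the first date of objectively determined PD or death from any cause". A patient alive at cut-off without evidence of tumor progression is handled thus: "PFS will be censored at the date of the most recent objective progression-free observation". A second rule applies to new treatment: "For patients who receive subsequent anticancer therapy prior to objective disease progression or death, PFS will be censored" at the last progression-free observation before that therapy. Time to progression censors, at the last tumor assessment, patients lost to follow-up and those who "died without progression or reached the time point of analysis without a known record of progression".

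**Status of clinical progression.** The note to Appendix 2 Table 1 classes symptomatic deterioration as a reason to stop therapy but not as objective progression, and asks for objective documentation even after discontinuation.

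**The concern.** A site that follows 12.10.1 stops imaging exactly those patients whose progression is most obvious. A site that follows 11.1 scans them. The two sites would produce different PFS and time-to-progression data from the same clinical course, and scans never taken cannot be recovered in the analysis.

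Without a scan, 13.5.4 has no progression event to count. The patient either contributes a later event (death) or leaves the risk set at her last good scan. Leaving in this way is informative, because the reason assessment ended is the progression itself. Both routes push the Kaplan-Meier curve up. At stake are two secondary efficacy endpoints that describe how long disease control lasts.

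**Working it through.** **Step 1. Trace the unscanned clinical progressor through 13.5.4.**

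| What happens next | PFS | Time to progression |
|---|---|---|
| Dies before cut-off, no new therapy | Event, dated at death (late) | Censored at last scan |
| Starts new anticancer therapy | Censored at last progression-free scan before it | Censored at last scan |
| Alive at cut-off, no new therapy | Censored at last scan, if regarded as without evidence of tumor progression | Censored at last scan |

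The last PFS cell is ambiguous: the wording does not settle whether a clinical progressor counts as having no evidence of progression.

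**Step 2. Inputs for an illustration.** The protocol states no PFS or time-to-progression figure, event count or power, so there is nothing to reproduce.

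- Scan interval: 8 weeks (11.1), so w = 56/30.4375 = 1.840 months; the third scan falls at 5.52 months.
- Median time to progression: 3.5 months, assumed, as the midpoint of the 3-4 months cited in section 1.2. Exponential, with rate a = ln 2/3.5 = 0.198 per month.
- Share f of progressors never scanned: not given; 10%, 20% and 30% assumed.
- Median survival s after clinical progression: not given; 1, 2 and 6 months assumed, exponential, with rate b = ln 2/s.

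**Step 3. Reference.** If all progressions are found at scheduled scans, the 6-month estimate is the share still progression-free at the third scan: exp(-0.198 × 5.52) = 33.5%.

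**Step 4. Time-to-progression rule.** The chance of progressing within one scan interval is p = 1 - exp(-a·w) = 0.3054. Unscanned progressors are censored at the previous scan, so the hazard seen at each scan is h = (1 - f)p/(1 - fp), and the 6-month estimate is (1 - h)³.

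- f = 10%: h = 0.2835, estimate 36.8%
- f = 20%: h = 0.2602, estimate 40.5%
- f = 30%: h = 0.2353, estimate 44.7%

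The same figures apply to PFS if every unscanned progressor starts new therapy.

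**Step 5. PFS rule, no new therapy.** An unscanned progressor is an event at death, and follow-up is taken as long enough to see it. The chance that she has no event by 6 months is P = [b·exp(-6a) - a·exp(-6b)]/(b - a), and the estimate is (1 - f) × 33.5% + f × P.

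| Median survival after clinical progression | P | f = 10% | f = 20% | f = 30% |
|---|---|---|---|---|
| 1 month | 42.0% | 34.4% | 35.2% | 36.1% |
| 2 months | 54.4% | 35.6% | 37.7% | 39.8% |
| 6 months | 77.3% | 37.9% | 42.3% | 46.7% |

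**Step 6. Other medians.** With f = 30%, the time-to-progression estimate rises from 27.9% to 38.8% for a 3-month median, and from 38.4% to 49.7% for a 4-month median.

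**The case against.** **Section 12.10.1 is a safety-reporting section.** It tells sites what not to report as AEs, and it keeps the duty to seek objective documentation. Sections 6.1, 6.2 and 11.1 govern imaging and are explicit. This is fair, and it means the text is not a free licence to skip scans. But the protocol does not say which section prevails, and the duty to make every effort does not cancel the permission that follows it.

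**Death is a PFS event.** A reader might infer that PFS counts objective progression alone and that every obvious progressor is censored as progression-free at her last good scan. Section 13.5.4 does not support that: a patient who dies before cut-off without new therapy is an event. Late dating remains, and if survival after clinical progression is short the effect is small (1 to 3 percentage points with a 1-month median). Time to progression has no such protection. Nor is capture of these deaths expressly secured, since section 5.5.8 assigns survival calls to patients with RECIST progression and scans to the rest.

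**Counting only objective progression or death is a deliberate definition.** That stands, and the definition is not the fault. The fault is that the protocol gives opposing instructions on whether the data it needs are collected.

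**A sensitivity analysis may already be in the SAP, which is not to hand.** True, and its absence from the protocol is no defect. It is part of the remedy; the contradiction is the finding.

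**Conclusion.** The contradiction between 12.10.1 and sections 6.1, 6.2 and 11.1 is real, and the protocol must be reconciled. Its consequence is a risk of upward bias in PFS and time to progression. The direction is clear; the size is not. It rests on the share of progressors left unscanned and on survival after clinical progression, neither of which is stated, and on how many start new therapy. Over the assumed ranges, 6-month time to progression moves from about 33.5% to 37-45%, and 6-month PFS to between 34% and 47%.

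Three stronger readings are not supported. That PFS is overstated cannot be said, because nothing in the protocol shows that any patient will go unscanned. That the bias differs between the 500 and 750 mg/m² cohorts is possible in an open-label study, but nothing in the text indicates it. And the study's success rule is untouched: it rests on confirmed responses by blinded independent central review and does not use PFS censoring. PFS and time to progression are secondary and carry no stated success threshold. The point is therefore a worthwhile correction that does not threaten the primary conclusion.

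**What to change.** 1. Reconcile 12.10.1 with 6.1, 6.2 and 11.1, so that a single statement says whether disease assessments continue when progression is suspected or clinically evident. Which rule applies is for the sponsor and investigators to settle.
2. Record the date of clinical progression on the CRF, for example on the existing Treatment Discontinuation page.
3. Report, by dose level, how many patients had clinical progression without objective documentation, and how each was handled for PFS and for time to progression (event at death, censored at new therapy, censored at cut-off).
4. Add, or confirm in the SAP, a sensitivity analysis of both endpoints that counts undocumented clinical progression as an event on its recorded date.

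The cost is a wording change, one CRF date and one extra analysis. Sample size and the primary analysis do not change.

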12.10.2 Death on Study Attributed to Malignancy

Death due to disease under study is to be recorded on the Death CRF form, provided that the death is not unexpected and no causal relationship is suspected. The Investigator must clearly state whether the death was expected or unexpected and whether a causal relationship to NUC-1031 or other protocol treatment intervention is suspected.

12.10.3 Elective Admissions and Supportive Care

Elective admissions to hospital for patient convenience or for planned procedures or investigations or treatment as specified in this protocol and standard supportive care are not SAEs, and do not require SAE reporting.

12.11 Informing Investigators of New Safety Information

NuCana will ensure that all Investigators are kept informed, in a timely manner, as new safety information becomes available. Investigators are responsible for briefing their study team as appropriate.

12.12 Reference Safety Information (RSI) for Assessment of Expectedness

The IB supplied by NuCana for NUC-1031 contains a defined table, which will act as the RSI for the study. Only the IB version with current regulatory and IRB/EC approval for use in the study will be used to assess SAE reports to identify SUSARs.

- **Significant Changes to the RSI:** If patient safety or the risk/benefit assessment has changed or new expected reactions have been added, then approval of the updated IB by applicable Regulatory Authorities and IRBs/ECs will be sought. If new expected reactions have been added to the IB or events have downgraded to ‘expected’, a justification for the changes will be included in the amendment request. Changes to the IB that impact on patient safety or alter the risk/benefit assessment may require changes to the study documentation such as the ICF. NuCana will identify any such required changes and ensure ICF revisions are made and approved by applicable Regulatory Authorities and IRBs/ECs, and patients re-consented as applicable. Significant updates to the IB shall be attached to the DSUR (once approved by applicable Regulatory Authorities and IRBs/ECs); however the IB in effect at the start of the DSUR reporting period serves as the RSI during the reporting period.
- **Non-Significant Changes to the RSI:** If changes to the IB are minor and do not include new/removed expected reactions, do not impact on patient safety or alter the benefit/risk assessment, then sites will not receive the updated IB until the end of the DSUR reporting period and this decision will be made by NuCana.

If the non-significant updated IB is to be implemented in the new DSUR reporting period, then Regulatory Authority and IRB/EC should be informed of the intention to implement the updated IB after the DSUR reporting period ends. The updated IB will be attached to the DSUR. If new expected reactions have been added to the IB or events have downgraded to ‘expected’, then the updated IB must receive approval before it is implemented. The IB will be sent to the study sites with a covering letter documenting the changes. This will be circulated after the DSUR has been submitted at the start of the new DSUR reporting period.

12.13 Data Safety Monitoring Committee (DSMC)

The DSMC will review the safety, dosing intensity, pharmacokinetic and clinical activity data from Part I of the study to decide on which dose should be used in Part II. Members of the DSMC will include:

- Chief Investigators from the US and Europe
- Selected Principal Investigators from participating sites
- Chiltern Medical Monitors
- NuCana Medical Director
- Study management staff from NuCana.

